## 2. LAY SUMMARY

Hypertension Plus was developed to help patients measure their blood pressure (BP), send the results to the GP, and communicate about changes they could make to their treatment. Hypertension Plus reminds patients to measure their BP, and reminds patients and their GPs and other clinical staff when they need to take action.

The NIHR Applied Research Collaboration (Oxford and Thames Valley) is funding "A service evaluation of the implementation of Hypertension Plus" know as the "SHIP" study for short. The SHIP study will

explore how well Hypertension Plus works in GP surgeries, in particular how many patients choose to use it, how well their blood pressure is controlled, and what impact it has on the workload of GP practices.we will look at the impact on the cost of care, and how many prescriptions are issued.

The SHIP study will use anonymised routinely collected data, recorded by practices and patients in their routine care. We will compare data from patients who have chosen to useHypertension Plus with those who haven't. For those patients who use Hypertension Plus, we will compare results from before and after they start to use it. There is no way of the research team knowing who the patients are.

Summaries of the results will be shared with GP practices, patients and commissioners of care. The research team will publish the results in journals and present at conferences and share them in traditional and social media.

# 3. SYNOPSIS

Study Title	A Service evaluation of the Hypertension-Plus Implementation – implementing a hypertension self-monitoring/management service in primary care				
Internal ref. no. / short title	The SHIP study				
Study registration	tbc				
Sponsor	University of Oxford Joint Research Office [name]				
Funder	NIHR ARC Oxford and Thames Valley [name] [name] [name] [contact] Email: arc. [contact]				
Study Design	Observational Service	e Evaluation			
Study Sites	GP practices				
Study Participants	Adult patients (>18y) with hypertension				
Sample Size	Anonymised records	from approximately 60 practices			
Planned Study Period	From January 2022 fo following recruitment	er around 12 months with follow-up t.	o for 12 months		
	Research Questions	Outcome Measures	Timepoint(s)		
Primary	Does Hypertension Plus lead to lower systolic blood pressure?Systolic blood pressure of system us compared to before and o patients		Over the first year of system use compared to year before and control patients		
Secondary	Will people with hypertension use the HypertensionProportion of hypertension register signing up for Hypertension Plus in first 6 months of implementation in each practice.Over the first ye of system use				
	Does Hypertension Plus lead to lower diastolic blood pressure?Diastolic blood pressureOver the first year of system use compared to year before				

	Does Hypertension Plus lead to better control of blood pressure?	Proportion controlled below target	Over the first year of system use compared to year before
	Does Hypertension Plus reduce practice workload?	Consultation rate recorded in clinic record before and after use of Hypertension Plus system	Over the first year of system use compared to year before
Intervention	Hypertension Plus system		
Comparator	We will use both interrupted case series (before/after) and difference of differences approaches meaning that the comparator is usual care without the use of Hypertension Plus. Practices that implement the system later will be used to as a further level of comparator.		

## 4. ABBREVIATIONS

ARC	Applied Research Collaboration		
BAME	Black and minority ethnic		
CI	Chief Investigator		
CRF	Case Report Form		
CTRG	Clinical Trials & Research Governance, University of Oxford		
EHR	Electronic Health Records		
GCP	Good Clinical Practice		
GP	General Practitioner		
HRA	Health Research Authority		
ICF	Informed Consent Form		
LTCs	Long term conditions		
NIHR	National Institute for Health Research		
NHS	National Health Service		
RES	Research Ethics Service		
PI	Principal Investigator		
PIL	Participant/ Patient Information Leaflet		
QoF	The Quality and Outcomes Framework		
R&D	NHS Trust R&D Department		
REC	Research Ethics Committee		
SOP	Standard Operating Procedure		

## 5. BACKGROUND AND RATIONALE

Hypertension is the key risk factor globally for death and disability and in the UK is the commonest long term condition currently recognised in over 8 million adults (14%). The pre-eminence of hypertension in cardiovascular prevention arises from its association with the most costly conditions to treat in health systems, namely stroke, ischaemic heart disease, heart failure, and dementia. Blood pressure reduction is associated with significant reductions in cardiovascular risk: every 5mmHg systolic pressure reduction will reduce CHD rates by 20% and stroke rates by 10% but a large evidence base shows that system failure, clinical inertia and reduced patient adherence lead to sub-optimal use of proven interventions, notably antihypertensive medication.

Key interventions which overcome all three issues, and have been shown to be cost-effective, are patient self-monitoring and self-management. Both have the particular value of high patient engagement and increased self-efficacy plus engage clinicians to address medication changes, achieving improved blood pressure control mainly through better management of medication, and show these gains without adding to healthcare utilisation and therefore cost.

Patient self-monitoring and facilitated self-management of hypertension, has the further opportunity to act as a model for how greater patient involvement in care might be translatable into other important conditions that require monitoring and medication titration including diabetes, heart failure, asthma, and thyroid disease is the major impact long term conditions for the NHS and patients.

This project builds on twenty years experience of self-monitoring/management of hypertension and will evaluate the implementation into primary care of a digital intervention developed specifically from this experience. The intervention has been developed by Omron, a blood pressure monitor manufacturer, and designed to be used by a wide group of people with hypertension and their practices.

The Applied Research Collaboration includes Omron as commercial partner, academics, general practice, NHS England, Academic Health Science Networks and perhaps most importantly, people with hypertension.

	Research Questions Outcome Measures		Timepoint(s)
Primary	Does Hypertension Plus lead to lower systolic blood pressure?		Over the first year of system use compared to year before
Secondary Will people with hypertension use the Hypertension Plus system?		Proportion of hypertension register signing up for Hypertension Plus in first 6 months of project	Over the first year of system use
	Does Hypertension Plus lead to lower diastolic blood pressure?	Diastolic blood pressure	Over the first year of system use compared to year before
	Does Hypertension Plus lead to better control of blood pressure?	Proportion controlled below target	Over the first year of sytem use compared to year before
Does Hypertension Plus reduce practic workload?		Consultation rate recorded in clinic record before and after use of Hypertension Plus system	Over the first year of system use compared to year before
Exploratory	Further exploratory analyses will include sub groups (age, sex, deprivation, practice characteristics, individual CCG/PCN areas). We will also examine medication prescription and fidelity to the intervention using telemonitoring system data.		

# 6. OBJECTIVES AND OUTCOME MEASURES

# 7. STUDY DESIGN

This will be a service evaluation of the implementation of Hypertension Plus using interrupted case series and difference of differences to detect change in blood pressure and workload associated with the implementation of the Hypertension Plus system.

Anonymised data will be used to compare those using the intervention with historical data from themselves as well as from people not using the intervention.

Quantitative data will be extracted using electronic searches of practice computer systems, secure data transfer and the Omron Hypertension Plus system. Identifiable information will not be extracted.

## 7.1 The Hypertension Plus System

Hypertension Plus is a primary care remote hypertension management and medication titration platform. Based on workflow algorithms proven in randomised controlled trials through the TASMIN studies, and decision-support tools compliant with NICE guidelines. Hypertension Plus is intended to facilitate remote population health management, improving outcomes and increasing efficiency of hypertension management in primary care.

The system combines a web based dashboard for professionals, which both reads and writes data to the practice clinical system, with a mobile phone "app" which is downloaded by participating patients and used to upload blood pressure and other information.

## 7.2 Implementation of the Hypertension Plus system

Implementation of the Hypertension Plus system is being led by Omron working with the National Association for Primary Care and Ernst & Young. They have a detailed implementation plan that has been developed independently comprising pre-implementation, implementation, initiation and maintenance phases. In undertaking this work they are working with the primary care networks and clinical commissioning groups that are implementing Hypertension Plus.

Once a primary care organisation has decided to commission Hypertension Plus (which is a paid for service), they will choose the practices to implement the system and these practices will work with the implementation group receiving training and initiation. The research team will be introduced to participating practices and research initiation will happen independently from the implementation.

The research team is working closely with the implementation to ensure that there is mutual understanding of the two types of activity.

#### Service evaluation procedures flow chart

# 8. PRACTICE IDENTIFICATION

# 8.1. Participating practices

We will work with approximately 60 GP practices (approximately 15 practices from each participating CCG) from areas that are taking part in the Omron Hypertension Plus first phase roll out and use a compatible Electronic Health Record (EHR) system. The precise number of practices will depend on the final number of practices in the first wave using an EHR system.

All participating practices must satisfy the following criteria:

- Practice is using (or planning to use) the Hypertension Plus telemonitoring system
- Utilises compatible EHR system
- Data available for the previous 2 years from practice recruitment are available

## 8.2. Exclusion Criteria: practices

• Practices that are not able to contribute data.

# 8.3. Study Patient Records

TM101-A

Protocol Template for a Research Study\_version 15.0 CONFIDENTIAL
© Copyright: The University of Oxford and Oxford University Hospitals NHS Foundation Trust 2019 Page 13 of
28

Outcome data for adult patients (>18 y) and on the hypertension register will be extracted from the EHR at each participating practice by electronic search and provided in an anonymised form to the analysis team.

Active users of the intervention will be defined as:

- Adults aged 18 years or above.
- Diagnosed with hypertension on practice hypertension registers whose baseline blood pressure is above 140/90mmHg on last recorded reading at baseline
- Registered users of the Hypertension Plus telemonitoring system with coded data in the clinical record identifying them as such

These will be compared to patients not using the system who are:

- Adults aged 18 years or above
- Diagnosed with hypertension on practice hypertension registers whose baseline blood pressure is above 140/90mmHg on last recorded reading at baseline
- With no record of using the Hypertension Plus telemonitoring system coded in the clinical record.

An exploratory analysis will examine people in the two groups above who have a blood pressure  $\leq$ 140/90mmHg at baseline, with the same comparison between users and non users of the system.

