## 9.6. Data Extraction

Routinely collected retrospective data from people with a clinical code for hypertension registered in practices taking part in the Hypertension Plus implementation will be extracted at baseline and again at 6 and 12 months. This data will include:

- Age (years)
- Gender
- Ethnicity (White, Black, Asian, Mixed, Other)
- Smoking status (current, ex or non)

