#### Timeframe of outcome measurement

"Time 0" for exposed patients will be the date on which they start using the Hypertension Plus monitoring system. For unexposed patients "Time 0" will be the median date on which exposed patients in the same general practice started using the Hypertension Plus system. Longitudinal data for all TM101-A

Protocol Template for a Research Study\_version 15.0CONFIDENTIAL© Copyright: The University of Oxford and Oxford University Hospitals NHS Foundation Trust 2019Page 17 of28

outcomes (BP measurements, consultation dates etc.) will be extracted from patient's electronic health record from the 12 months before and after "Time 0" for all patients.

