#### Covariates

Covariates will be any factors that may confound the relationship between use of the Hypertension Plus system and the primary outcome which have been identified from our previous research. These are:

- Age (years)
- Gender
- Ethnicity (White, Black, Asian, Mixed, Other)
- Smoking status (current, ex or non)
- Index of Multiple Deprivation
- Body mass index (kg/m^2)
- Total cholesterol (mmol/L)
- Systolic and diastolic blood pressure (clinic or home readings)
- Past medical history:
  - Diagnosis of diabetes (Type 1 or 2)
  - Previous myocardial infarction or stroke
  - Diagnosis of chronic kidney disease
  - Estimated glomerular filtration rate (eGFR, ml/min/1.73 m^2)
- Medication use:
  - Statin treatment (drug type and dose)
  - o Antihypertensive medication use (drug type and dose, defined daily dose)
  - o Other current cardiovascular medication
- Electronic Frailty Index and/or characteristics making up the electronic frailty index
- Health Economic Resource use including consultation rate, timing, personnel undertaking, referrals and admissions.

Covariates will be defined using the closest available electronic healthcare records data prior to "Time 0" for all patients, but within the previous two years. Otherwise this data will be regarded as missing.

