## Subgroup analysis

Analyses and modelling above will be repeated in the following subgroups:

• Men and women

TM101-A

Protocol Template for a Research Study\_version 15.0CONFIDENTIAL© Copyright: The University of Oxford and Oxford University Hospitals NHS Foundation Trust 2019Page 19 of28

- Age >65 years; >80 years
- Mean SBP before "Time 0" (>160 mm Hg)
- Previous history of myocardial infarction or stroke
- By CCG area
- Users of the system for at least 6months defined as coded data identifying use recorded in the clinical record at both baseline and between months 6-12
- People with baseline blood pressure ≤140/90 compared to those >140/90mmHg
- Deprivation score (High vs Low)
- Ethnicity

Sample size requirements for this study were determined through simulation, as there is little statistical literature for sample size requirements for multilevel modelling. Data was simulated for systolic BP measurements, nested within patients, nested within practices, with the same structure as that detailed in the statistical modelling section. Normal distributions for BP values and variances around patient and practice mean values were assumed (reflecting random intercept terms). A global mean BP of 148 mm Hg was assumed, with practice variation (standard deviation, SD) of 5 mm Hg about this mean. Within a practice, patient variation (SD) was assumed as 17 mm Hg and measurements within a patient were assumed to vary by 10 mm Hg (SD) about the patient mean. The effect of time was assumed to be 0, clinic BP measurements were assumed to be 5 mm Hg higher than home measurements and 25% of patients were expected to take up the Hypertension Plus system.

Assuming an effect size of -3 mm Hg (BP 3 mm Hg lower in patients using the Hypertension Plus system) and a minimum of 4 BP measurements for each patient, 1000 simulated datasets were created and multilevel models as described in the statistical modelling section were fitted to each simulation. This demonstrated that to achieve 90% power at the 5% significance level for the effect of the Hypertension Plus system, 100 patients each drawn from 8 general practices would be required for this study (800 patients in total, 91% power).

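### The 140/90 entry reading is not tied to Time 0, so for some users it can be a reading taken after they started the system

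*Protocol*

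**What the plan says.** Section 8.3 applies one BP criterion to users and non-users: "Diagnosed with hypertension on practice hypertension registers whose baseline blood pressure is above 140/90mmHg on last recorded reading at baseline". Patients at or below 140/90 go to an exploratory comparison. Section 12 takes all eligible patients into the primary analysis, so this criterion decides who is in it.

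Section 8.3 does not say when baseline is. Section 9.6 says data "will be extracted at baseline and again at 6 and 12 months", which makes baseline the first extraction round. Section 8.1 accepts a practice if "Practice is using (or planning to use) the Hypertension Plus telemonitoring system" is true of it, and section 9.1 invites practices on the same terms. Section 7.2 adds that "research initiation will happen independently from the implementation".

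Section 11.2 has a defined anchor. Time 0 "for exposed patients will be the date on which they start using the Hypertension Plus monitoring system"; for non-users it is the median start date of users in the same practice. Exposure, the outcome windows and the covariates all hang on Time 0. For covariates the wording is explicit: "Covariates will be defined using the closest available electronic healthcare records data prior to" Time 0, within two years. The entry BP is the one key variable without this anchor.

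**The concern.** In a practice that is live before its first extraction, a user's last reading at that extraction may have been made on the system. The 140/90 rule then selects users partly on the outcome the study measures. Users already brought to 140/90 or below move to the exploratory group, where they look as if they had been controlled before starting. Non-users may also be judged on a reading after their own Time 0, but theirs carries no system effect.

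Section 12.3 answers regression to the mean by choosing both groups on the same attributes. That does not help here: the attribute is nominally the same, but it is post-treatment in users only. The primary SBP effect and the BP-control effect are both exposed.

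**Working it through.** **The plan's own figure.** The number that rests on the entry rule is 336 eligible patients per practice: 8000 × 0.14 × 0.30 = 336. It reproduces. The plan gives no figure for the selection effect.

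**Inputs from the sample-size text in 11.2.** Mean SBP 148; SDs 5 (practice), 17 (patient), 10 (within patient); clinic readings 5 above home; effect -3 mm Hg.

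**Assumptions.** SBP criterion only. The 148 and the SDs describe patients before the criterion is applied. Two readings before and two after Time 0 (the plan says at least four in all). The qualifying reading is one of the two after. The home-clinic offset affects the qualifying reading but is adjusted out of the analysed values. All users start before the extraction, which is the upper case. The effect is estimated as a difference in patient mean changes.

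**Step 1: who passes.** Total SD T = √(25 + 289 + 100) = 20.35. The proportion above 140 is 1 − Φ((140 − mean)/T):
- before start, mean 148: 65.3%
- after start, clinic reading, mean 145: 59.7%
- after start, home reading, mean 140: 50.0%

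**Step 2: who is lost.** Two readings in one patient correlate at 314/414 = 0.758. Among patients above 140 on a reading before start, the bivariate normal probability that a later reading is 140 or below is:
- no shift (chance alone): 16.0%
- effect only (-3): 21.0%
- home offset only (-5): 24.8%
- both (-8): 31.1%

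So 31.1 = 16.0 chance + 8.8 home-clinic offset + 6.3 system effect. On a clinic reading the system's part is 21.0 − 16.0 = 5.0 points.

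**Step 3: effect on the estimate.** Let a = (140 − mean)/T and λ = φ(a)/(1 − Φ(a)). Selection raises the mean error of the qualifying reading by e = (100/T)λ. If response varies with SD s, then T² becomes 414 + s², and the mean response in those selected is δ = -3 + (s²/T)λ. With w the qualifying reading's share of the post-start mean, DiD = δ + w·e (users) − w·e (non-users). For non-users, a = -0.393, λ = 0.566, e = 2.78. With w = 1/2 in both groups:

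| Users | T | λ | δ | e | DiD |
|---|---|---|---|---|---|
| s = 0, clinic | 20.35 | 0.648 | -3.00 | 3.19 | -3.00 + 1.59 − 1.39 = -2.80 |
| s = 0, home | 20.35 | 0.798 | -3.00 | 3.92 | -3.00 + 1.96 − 1.39 = -2.43 |
| s = 5, clinic | 20.95 | 0.652 | -2.22 | 3.11 | -2.22 + 1.56 − 1.39 = -2.05 |
| s = 5, home | 20.95 | 0.798 | -2.05 | 3.81 | -2.05 + 1.90 − 1.39 = -1.54 |

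Simulation with 1.5 million patients per group gives -2.79, -2.40, -2.07 and -1.53. With entry on the last reading before Time 0 it gives -2.98 to -3.03.

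**Step 4: direction.** The response term δ always moves towards zero. The error term need not. If users have about 20 post-start readings (assumed), then w = 1/20 for them and their term is 0.05 × 3.19 = 0.16, against 1.39 for non-users. That pushes the estimate beyond -3. A simulation with 20 home readings per user, 1 to 4 clinic readings a year and extraction 3 to 6 months after Time 0 (all assumed) gave -2.7 and -3.4 with a uniform effect, and -1.7 and -2.6 with SD 5.

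**Sensitivity to the mean.** The plan also puts uncontrolled hypertension at 30%. With SD 20.35 that implies a mean of 140 − 0.524 × 20.35 = 129.3. Step 3 with a uniform effect then uses e = 5.70 for non-users and 6.24 (clinic) or 7.17 (home) for users: -3 + 3.12 − 2.85 = -2.73 and -3 + 3.59 − 2.85 = -2.26. The picture is similar.

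**The case against.** The strongest reply is that baseline may simply have been meant as Time 0. Section 9.6 is an extraction schedule and does not say that entry BP is read at the first extraction. The covariate list in 11.2 includes systolic and diastolic pressure, fixed before Time 0. The summary statistics and the high-SBP subgroup also use BP before Time 0. The six-month-user subgroup, with "coded data identifying use recorded in the clinical record at both baseline and between months 6-12", fits baseline as the start of use at least as well as a later extraction. This stands as a possible reading, but 8.3 does not state it. Nor would it clear everything: Time 0 is the day use starts, so the reading at baseline could be the first app reading, judged against the same 140/90 as a clinic reading.

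It is also fair that section 7.2 separates two activities and states no delay, that the share of practices already live is unknown, and that patients at or below 140/90 are still analysed, in the exploratory comparison.

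Three stronger readings are tempting and are not supported:
- That responders do drop out of the primary analysis. The text permits this; it does not establish that it will happen, or how often.
- That the roughly 31% who fail entry on a home reading are responders. Only 5 to 6 points are due to the system.
- That the effect must shrink. With a uniform effect the direction depends on reading counts that the plan does not fix.

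The point is not a detail to leave to a later analysis plan. Section 8.3 fixes the eligibility rule, and section 11.1 makes a separate plan optional.

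**Conclusion.** The concern holds in a conditional form. As written, the entry reading can fall after a user has started, because 8.3 leaves baseline unanchored, 9.6 makes it an extraction round, and practices already live are admitted. If this held for all users, a true -3 mm Hg would be estimated at about -2.8 to -2.4 with a uniform response under equal reading counts (-2.7 to -3.4 under the unequal counts simulated), and at about -2.1 to -1.5 under equal counts if response varies with SD 5, a figure the documents do not give. These are upper-case values. The actual bias is scaled down by the share of users who start before the first extraction, which is not stated, and it may be small. It would largely vanish if baseline means Time 0. The change is worth making because the better rule is already in the protocol for covariates and costs little.

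**What to change.** In section 8.3, for users, non-users and the exploratory group at or below 140/90, replace the reference to the last recorded reading at baseline with the last reading recorded before Time 0. Add that no reading on or after Time 0 determines entry, including in practices already live when recruited. Use the same definition for the 140/90 subgroup in 11.2.

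The cost is a date condition in the cohort query. Practices that went live long before recruitment may lack enough earlier data, because section 8.1 counts its two years of data back from recruitment and not from go-live. A few of them might be lost.
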